12.2 Sample size

12.2.1 Sample size for primary safety endpoint

In the St. Jude Medical Accent MRI pacemaker IDE study, the results of which were submitted in PMA 60067410/A, and another manufacturer's study involving an MRI conditional pacemaker, the complication-free rate was observed to be 100%.^{16,14}

Therefore, the sample size is calculated under the conservative assumption of

Clinical Investigational Plan

complication-free rate of 97%. Under this assumption, a sample size of 141 subjects will provide 90% power to reject the null hypothesis at a 2.5% significance level. The sample size was calculated using the exact binomial method in SAS® v9.4.

12.2.2 Sample size for primary efficacy endpoint #1 (Change in capture threshold for Durata or Optisure (RV) lead)

In the St. Jude Medical Accent MRI pacemaker IDE study, the results of which were submitted in PMA 60067410/A, the proportion of leads with an increase in threshold ≤ 0.5 volts from pre-MRI scan testing to 1-Month after the MRI scan was 100%.^{1,2}. Therefore, the sample size is calculated under the conservative assumption of 98% for the endpoint. Under this assumption, a sample size of 85 subjects will provide 80% power to reject the null hypothesis at a 2.5% significance level. The sample size was calculated using the exact binomial method in SAS® v9.4.

12.2.3 Sample size for primary efficacy endpoint #2 (Change in sensing threshold in Durata or Optisure (RV) lead)

In the St. Jude Medical Accent MRI pacemaker IDE study, the results of which were submitted in PMA 60067410/A, the proportion of leads with ‘ventricular sensing amplitude decrease of $\leq 50\%$ from pre-MRI scan testing to 1-Month after the MRI scan,’ was approximately 97%. Therefore, the sample size is calculated under the conservative assumption of 95% success rate for the ventricular sensing threshold endpoint. Under this assumption, a sample size of 118 subjects will provide 80% power to reject the null hypothesis at a 2.5% significance level. The sample size was calculated using the exact binomial method in SAS® v9.4.

12.2.4 Overall Sample Size

Up to 165 subjects will be enrolled in this study in order to meet minimum target requirements for primary safety endpoint #1. The sample size estimate of 165 subjects is based on 15% attrition rate. ($141/0.85=165$).

12.2.5 Analysis

The dataset will be frozen for analysis when 141 subjects have completed the 1 month post MRI visit and a minimum of 25 subjects with at least one ventricular arrhythmia event (spontaneous or induced) are adjudicated by the Ventricular Arrhythmia Events Committee. If a minimum of 25 subjects have not experienced a ventricular arrhythmia event (spontaneous or induced) at this time, SJM will discuss progress of data collection for ventricular arrhythmia events with FDA to support the minimum requirements to support a pre-market approval (PMA) application.

Clinical Investigational Plan

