4.2.2 Estimated Time Needed to Enroll Subject Population

Enrollment in this clinical study is expected to take approximately 12 months. The anticipated duration of this study is 1.5 to 2 years, depending on the rate of enrollment and regulatory timelines.

The minimum duration of each subject's participation, if he/she undergoes an MRI scan, in the study is 23 days. All subjects will have the Durata or Optisure lead implanted for at least 60 days prior to enrollment.

The following study visits will occur after enrollment:

- MRI scan/Post Scan testing
- 1 Month Post Scan visit

The MRI Scan should take place no sooner than 60 days post lead implant or lead revision procedure where the Durata or Optisure lead was implanted or repositioned. The 1 Month Post Scan visit is based on the MRI Scan Visit.

Clinical Investigational Plan

A data collection effort to collect VT/VF events will also take place. For subjects on Merlin.net, the Merlin.net records will be reviewed for spontaneous VT/ VF events. Subjects not on Merlin.net will be contacted by phone and their medical records will be screened every 3 months for VT/VF events since the last visit. The data collection effort will end upon notification from SJM.

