12.1.1 Primary Safety endpoint

The primary safety endpoint #1 is: Freedom from MRI scan-related complications related to the Ellipse VR ICD involving Durata or Optisure (RV) lead from MRI scan to 1 month post MRI scan testing.

Hypothesis

The hypothesis is formally expressed as:

$$H_0: p_S \leq 90\%$$

$$H_a: p_S > 90\%$$

where p_S is the freedom from MRI scan-related complications(s) for the Durata or Optisure RV lead from MRI scan to 1 month after the MRI scan.

Analysis

The primary analysis will be conducted on subjects who meet all of the following criteria:

- Implanted with St. Jude Medical Durata or Optisure (RV) Lead
- Sign informed consent
- Meet the MRI Conditions of Use
- Undergo a Study MRI scan
- Have 1 month post-MRI scan visit or have MRI-scan related complication(s) for the Ellipse VR ICD involving Durata or Optisure RV lead before the 1 month post MRI visit

Clinical Investigational Plan

The hypothesis will be tested at the 2.5% significance level. The null hypothesis will be rejected if the 97.5% lower confidence bound for p_S is greater than 90%. The 97.5% lower confidence bound will be calculated by the exact (Clopper-Pearson) method for binomial probabilities.

12.1.2 Primary Efficacy Endpoint #1 (Change in Capture Threshold for Durata and Optisure (RV) Leads)

The primary efficacy endpoint #1 is the proportion of Durata or Optisure (RV) leads implanted with the Ellipse VR ICD with capture threshold increase of $\leq 0.5V$ at 0.5ms from pre-MRI scan to 1 month post-MRI scan testing.

Hypothesis

Success is defined as ventricular capture threshold increase of $\leq 0.5V$ at 0.5ms for the Durata or Optisure (RV) lead from pre-MRI scan testing to 1 month post-MRI scan.

The hypothesis is formally expressed as:

$$H_0: p_{E1} \leq 90\%$$

$$H_a: p_{E1} > 90\%$$

where p_{E1} is the probability of success.

Analysis

The primary analysis will be conducted on subjects who meet all of the following criteria:

- Implanted with the Durata or Optisure RV lead and Ellipse VR ICD
- Sign Informed consent
- Meet the MRI Conditions of Use
- Undergo a Study MRI scan
- Have MRI visit data for right ventricular capture threshold
- Have 1 month post-MRI scan visit data for RV capture threshold
- Have not undergone any VR ICD lead repositioning or replacement since the MRI scan up to 1 month post-MRI scan

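### The freeze rule in 12.2.5 does not say what happens to scanned subjects still awaiting the 1-month visit; as written, they enter the safety set only if they have failed

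*Combined protocol and SAP*

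**What the plan says.** Section 12.2.5 sets the cut-off: "The dataset will be frozen for analysis when 141 subjects have completed the 1 month post MRI visit". A second requirement is joined to it by 'and': at least 25 subjects with a ventricular arrhythmia event adjudicated by the committee. If those 25 are not available at that time, the sponsor is to discuss progress with FDA.

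Section 12.1.1 defines who is analysed for safety. A scanned subject needs either a 1-month visit or MRI-related "complication(s) for the Ellipse VR ICD involving Durata or Optisure RV lead before the 1 month post MRI visit". For the two efficacy endpoints, 12.1.2 and 12.1.3 require 1-month capture or sensing data.

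On numbers, 12.2.4 says "Up to 165 subjects will be enrolled in this study", obtained from 141 by allowing 15% attrition. Section 4.2.2 says "Enrollment in this clinical study is expected to take approximately 12 months". The 1-month visit is at 30 days, with a window of -7 to +14 days (Table 5).

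The protocol does not say that subjects already scanned at the trigger are followed to 1 month before the freeze. Sections 12.8 to 12.10 refer the use of all data, missing data and exclusions to a separate statistical analysis plan, which is not part of the text reviewed here.

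**The concern.** Read together, the two rules treat the last subjects scanned unequally. If such a subject already has a complication at the freeze, one failure is added to the numerator of failures and one subject to the denominator. If the subject is event-free so far, nothing is added. The complication-free rate is then estimated with some failures whose matching successes are missing. The same subjects' capture and sensing results are not used, although they have been exposed to the scan.

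What is at stake is an unbiased safety estimate in a single-arm trial, some of the margin in its power, and the use of exposure that subjects have already undergone.

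**Working it through.** **Inputs.** From 12.1.1: null rate 90%; one-sided test level 2.5%; "The null hypothesis will be rejected if the 97.5% lower confidence bound for p_S is greater than 90"%, the bound being "calculated by the exact (Clopper-Pearson) method for binomial probabilities". From 12.2.1: an assumed "complication-free rate of 97"% and N = 141 for 90% power. Two quantities are not in the documents and are assumptions here:
- *m*, the number scanned but not yet at the 1-month visit at the freeze (range 0 to 24);
- *g*, the share of those subjects' eventual complications already adjudicated at the freeze (shown at 1 and 0.5).

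**The plan's own figure.** With 134 of 141 complication-free, the exact lower bound is 90.04%, so up to 7 failures pass. Power is P(Bin(141, 0.03) ≤ 7) = 93.7%, and type I error is P(Bin(141, 0.10) ≤ 7) = 2.42%. At N = 140 only 6 failures pass and power is 87.1%. So 141 reproduces if 90% means at least 90%, and it leaves 3.7 points to spare.

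**How many are in follow-up.** Two bounds apply.
- Flow: 165/12 = 13.75 a month, which is about 14 over 30 days or about 20 over 44 days.
- Cap: subjects still to complete after the 141st are 165 × (1 − attrition) − 141. This is 24 at 0%, about 16 at 5%, about 7 at 10%, and none at the planned 15% (165 × 0.85 = 140.25).

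For 14 to remain, attrition must be no more than 1 − 155/165 = 6.1%. If the arrhythmia condition is met after the 141st visit, some or all of these subjects will have completed by the freeze.

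**Effect on the rate (g = 1).** The expected observed rate is approximately 141 × 0.97 / (141 + 0.03*m*). For *m* = 14 this is 136.77/141.42 = 96.7%. For *m* = 24 it is 136.77/141.72 = 96.5%.

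**Effect on power.** With *x* failures among the *m*, the analysed N is 141 + *x*. Let c(N) be the largest number of failures that passes at N. Then

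power = Σₓ P(Bin(*m*, 0.03*g*) = *x*) × P(Bin(141, 0.03) ≤ c(141 + *x*) − *x*).

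c(N) is 7 for every N from 141 to 153 and 8 from 154 to 166. At g = 1 the sum therefore reduces to P(Bin(141 + *m*, 0.03) ≤ 7). If everyone is followed, power is P(Bin(141 + *m*, 0.03) ≤ c(141 + *m*)).

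| *m* | Power as written, g = 1 | Power as written, g = 0.5 | Power if all followed | Type I error as written, g = 1 |
|---|---|---|---|---|
| 0 | 93.7% | 93.7% | 93.7% | 2.4% |
| 7 | 92.1% | 92.9% | 92.1% | 1.6% |
| 14 | 90.4% | 92.1% | 95.5% | 1.0% |
| 16 | 89.8% | 91.9% | 95.2% | 0.9% |
| 20 | 88.7% | 91.4% | 94.5% | 0.7% |
| 24 | 87.5% | 90.9% | 93.8% | 0.5% |

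At a true rate of 98%, power as written is at least 98.1% for every *m* up to 24.

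**Sensitivity.** The table lets a subject with a complication still attend the 1-month visit, as 6.8.2 mostly intends after a revision. In the extreme alternative no such subject attends and all 141 completers are event-free. Power is then 92.1% at *m* = 0, 88.6% at 14 and 85.6% at 24 (g = 1).

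**The case against.** The strongest reply has four parts.

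*The freeze is not at the 141st visit alone.* This stands. The arrhythmia condition may delay the freeze until everyone in follow-up has finished. But that would happen by chance, because nothing in 12.2.5 requires it.

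*At the planned 15% attrition nobody is left over.* This also stands as arithmetic. However, enrolment is counted only after eligibility is confirmed and the MRI settings are programmed (4.6.2), follow-up lasts about a month, and subjects who cannot tolerate the scan stay in the study (6.5.2.1). Lower attrition is therefore possible, and the rule should not depend on losing subjects.

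*A reader might infer that safety power drops below the stated 90%.* The documents do not support that as a general conclusion. In the main model it takes about 16 or more in follow-up, hence attrition of about 5% or less, with nearly all their complications already adjudicated. Sections 6.5.2.2 and 8.1.4 expect clotting, embolism and heating events to show during or just after the scan, which favours early recording. But 8.1.6 counts only complications adjudicated by the events committee, and adjudication may lag.

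*A reader might also infer that the open second condition lets the sponsor choose N after seeing results and so inflates type I error.* Section 12.2.5 gives a count and a discussion with FDA, not a free choice of N, and 12.4 plans no interim analysis. As written, the asymmetry lowers type I error.

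The separate analysis plan may define the cut-off cohort. If it does, the remaining task is to align 12.2.5 with it.

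**Conclusion.** The point holds as a defect in the freeze rule with a modest, conservative effect. Under 12.1.1 and 12.2.5 as written, a scanned subject still short of the 1-month visit at the freeze can enter the safety analysis only as a failure, and the efficacy data of such subjects go unused. At a true 97% the expected rate is understated by at most about 0.5 points. Main-model power falls from 93.7% to between 87.5% and 90.9% at the cap of 24 in follow-up, depending on whether all or half of their complications are adjudicated. With 14 in follow-up it stays between 90.4% and 92.1%. At the planned attrition there is no effect.

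These sizes rest on the assumed *m* and *g*. The error works against the sponsor, so a passing result would not be put in doubt. The rule should still be changed, because the correction is short and leaving out exposed, event-free subjects on visit timing alone has no justification in the text.

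**What to change.** In 12.2.5, keep the trigger, but state that the primary-endpoint data are frozen only when every subject scanned on or before the trigger date has completed or missed the 1-month visit. Define that date as the day of the 141st completed visit, so that the set is fixed by scan date. Analyse all these subjects under the existing criteria for the three primary endpoints. Let VT/VF collection continue towards 25 subjects without changing that set.

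**Cost.** A delay of at most about 44 days (30 + 14) and no additional subjects.

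**Gain.** The one-sided entry of in-follow-up subjects ends, and exposure already incurred is used. The power gain is uneven. With up to 12 in follow-up (N up to 153) the limit stays at 7 failures. Power then equals the as-written value with all complications adjudicated, and is slightly below the value with half adjudicated. From N = 154 the limit is 8, which gives 95.5% with 14 followed and 94.5% with 20. The case for the change is therefore the unbiased estimate rather than power.

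Subjects who miss the visit or drop out event-free are still left out under 12.1.1. That is a separate matter which this change does not settle.

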12.3 Pass/fail criteria to be applied to the results of the clinical study

The study will be considered successful if the primary safety and two primary efficacy endpoints are met.

12.4 The provision for an interim analysis

There are no planned interim analyses for the study

12.5 Criteria for the termination of the clinical study on statistical grounds

There is no planned termination for the study based on statistical grounds.

12.6 Procedures for reporting any deviation(s) from the original statistical plan

Refer to the statistical analysis plan for this study.

12.7 The specification of subgroups for analysis

Refer to the statistical analysis plan for this study.

12.8 Procedures that take into account all the data

Refer to the statistical analysis plan for this study.

12.9 The treatment of missing, unused or spurious data, including drop-outs and withdrawals

Refer to the statistical analysis plan for this study.

12.10 The exclusion of particular information for the testing of the hypothesis, if relevant

Refer to the statistical analysis plan for this study.

12.11 In multi-center studies, the minimum and maximum number of subjects to be included for each center

A minimum of 1 subject and a maximum of 41 subjects may be included at each center participating in the study.

Clinical Investigational Plan

13.0 Document Retention

St. Jude Medical and the Principal Investigators will maintain the clinical study documents as required by St. Jude Medical, Inc. and applicable regulatory requirements. They will take measures to prevent accidental or premature destruction of these documents. The Principal Investigator or St. Jude Medical may transfer custody of records to another person/party and document the transfer at the investigational site or at St. Jude Medical's facility.

These documents must be retained by the investigational site for a period of 2 years after clinical study conclusion and made available for monitoring or auditing by St. Jude Medical's representative or representatives of the FDA and other applicable regulatory agencies. The Principal Investigator must ensure the availability of source documents from which the information on the case report forms was derived.

14.0 Study Committee

14.1 Clinical Events Committee (CEC)/Ventricular Arrhythmia Event Review Committee (VAC)

The CEC is responsible for providing an independent review and adjudication of CIP pre-defined clinical events. The CEC will consist of at least 3 members. The CEC will be comprised of independent and unblinded physicians that are not investigators, DSMB members or steering committee members in the trial. St. Jude Medical will appoint members of the CEC and the chairperson. St. Jude Medical may facilitate the CEC meeting, but will not be voting members.

Reportable events to be collected under this protocol will be adverse device effects outlined in sections 8.1.2-8.1.6. The CEC will base their final adjudication on the information provided on the case report forms, medical records, and their clinical knowledge and experience. The CEC will also review and classify all subject deaths under this protocol. The primary function, responsibilities and membership of the CEC will be described in detail in a CEC charter .

The Ventricular Arrhythmia Event Review Committee (VAC) will review all device detected VT and VF episodes with a stored electrogram available and non-sustained VT/VF episodes of at least 16 beats. The members of the CEC will also be members on the VAC.

VT/VF episodes with at least 4 intervals ≥ 300 ms, with 1 interval ≥ 600 ms, or with the pre-detection time lasting more than 10 seconds, will be evaluated by the VAC for ventricular arrhythmia undersensing and amount of detection delay. A clinically significant detection delay is defined as ≥ 5 seconds.

Clinical Investigational Plan

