6.8 System Revisions

In cases where only the device pocket is revised (leads are not repositioned, leads have not been disconnected from the ICD), a System Revision CRF is not required to be submitted. A System Revision CRF should be completed for all other types of revisions such as pulse generator replacement, lead replacement and lead repositioning. The subject's follow up schedule is not affected in any way.

Clinical Investigational Plan

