8.1.6 MRI scan related complication

A complication is deemed to be MRI related if it is caused by or related to the interaction between the RV high voltage lead, Ellipse VR ICD and the MRI system that occurs during the MRI scan and includes the time the subject is within the 5 Gauss line of the MRI system, or up through the subject's 1 month post MRI scan follow up visit. The MRI scan related complications will be based on the CEC adjudication data.

8.2 Procedure for assessing, recording and reporting adverse device effects, serious adverse device effects and UADEs (for US sites) and USADEs (for OUS sites):

Safety surveillance within this study and the safety reporting, both performed by the investigator, starts as soon as the subject is enrolled in the study. Enrollment occurs after the subject signs the main study consent, meets all of the inclusion and none of the exclusion criteria verified during the pre-MRI testing, and the MRI Settings have been programmed. . The safety surveillance and the safety reporting will continue until the last investigational visit has been performed, the subject is deceased, the subject/investigator concludes his participation into the study or the subject/investigator withdraws the subject from the study, except as otherwise specified in the CIP.

Once the patient completes the pre-MRI visit testing and the MRI Settings have been programmed according to the protocol, all adverse device effects (whether serious or not-serious) UADEs and USADEs will be collected and reported to the Sponsor on an Adverse Event case report form through the EDC system.

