8.2.1 Criteria and guidelines for non-reportable events

Except as otherwise noted in the CIP, the following events are not reportable to the sponsor:

Clinical Investigational Plan

- Events not related to the procedure to remove, replace or reposition the study lead or ICD.
- Unavoidable events, as listed in Table 3: Unavoidable events related to the MRI Scan that resolve within the timeframes specified

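### The protocol gives the CEC only site-declared adverse device effects and deaths, so a post-scan revision that the site does not call an ADE need not be adjudicated for the primary safety endpoint

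*Combined protocol and SAP*

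**What the plan says.** Section 8.1.5 defines a complication as an SADE that leads to death or needs an invasive intervention. Section 8.1.6 adds the link to the scan and names the decision-maker: "The MRI scan related complications will be based on the CEC adjudication data".

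Section 14.1 describes the committee's material: "Reportable events to be collected under this protocol will be adverse device effects outlined in sections 8.1.2-8.1.6". It adds that the CEC classifies all deaths, and leaves further detail to a CEC charter. Under 8.1.2 an ADE is an adverse event related to use of the investigational device.

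Revisions have their own paperwork. Section 6.8 exempts pocket-only revisions and then says: "A System Revision CRF should be completed for all other types of revisions". Section 6.7 requires a Product Out of Service CRF for a complete explant but no System Revision CRF. In Table 5 (System Revision row) the site evaluates for ADEs and submits an AE CRF only where applicable. Table 9 does the same when the study lead is replaced after the scan and non-MRI-compatible material is implanted: System Revision and Withdrawal CRFs are to be submitted, an Adverse Event CRF only if applicable.

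On reporting, 8.2 and 8.2.2 make all ADEs and SADEs reportable, MRI-associated or not. Section 8.2.1 lists as non-reportable "Events not related to the procedure to remove, replace or reposition the study lead or ICD", subject to whatever the CIP says elsewhere.

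**The concern.** The trial is single-arm and open-label, and its safety claim rests on an independent committee. Apart from deaths, an event reaches that committee only after the site has judged it device-related. Relatedness is part of what an adjudicator should decide. It may also be judged differently across about 60 centers, because the devices are market-released and section 5.2 says the scan is the investigational element.

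Post-scan revisions matter most. Table 2 lists lead dislodgment, loss of capture or sensing, and tissue damage in the pocket among the potential MRI-related events, and each may lead to an invasive procedure. If the site puts the procedure down to something other than the device, the protocol records the revision but refers it to nobody. A missed complication raises the observed safety rate, which favors success. The efficacy analyses would not show the problem either, because both exclude leads repositioned or replaced after the scan (12.1.2, 12.1.3).

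**Working it through.** **Step 1. Trace one event.** Take a lead replaced two weeks after the scan, which the site does not call an ADE.

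- Forms: System Revision CRF, and Product Out of Service CRF for the explanted lead. No AE CRF, because none is applicable.
- CEC: not within the intake described in 14.1. No passage makes either form a trigger for review.
- Safety set (12.1.1): requires a 1-month visit or an MRI-related complication before it. With the visit, the subject counts as complication-free. Without it, the subject is out of the set.
- Efficacy sets (12.1.2, 12.1.3): the lead is excluded from both.

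The event can therefore count against no primary endpoint.

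**Step 2. Reproduce the plan's figure.** Inputs from 12.1.1 and 12.2.1: null 90%, assumed complication-free rate 97%, one-sided 2.5%, exact Clopper-Pearson bound. The stated result is that "a sample size of 141 subjects will provide 90% power to reject the null hypothesis at a 2.5% significance level".

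The lower bound for x complication-free subjects of n is the 0.025 quantile of Beta(x, n − x + 1).

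- n = 141, 7 complications (x = 134): 90.04%, pass.
- n = 141, 8 complications (x = 133): 89.13%, fail.

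Success therefore allows at most 7 complications. With X the number of complications:

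- Exact alpha = P(X ≤ 7 | 141, 0.10) = 0.0242.
- Exact power = P(X ≤ 7 | 141, 0.03) = 93.7%.

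Exact power moves in a saw-tooth. It first reaches 90% at n = 127, is 87.1% at n = 140, and from 141 on stays at or above 90% (checked to 259). The 141 is reproduced on that convention.

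**Step 3. Effect of one missed event.**

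- Subject stays in the denominator: 8 of 141 fails; with one unreferred it becomes 7 of 141 and passes.
- Subject drops out of the set: 8 of 142 fails (7 are allowed at 142), but 7 of 141 passes. This depends on n: 8 of 141 becoming 7 of 140 still fails, because only 6 are allowed at 140.

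**Step 4. Illustration of systematic loss.** Let m be the share of true complications that never reach the CEC. The documents give no value, so 10% to 30% is an assumption. With affected subjects kept in the denominator, the pass probability is P(X ≤ 7 | 141, q(1 − m)), where q is the true complication rate.

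| m | q = 10% (null) | q = 12% | q = 3% (planned) |
|---|---|---|---|
| 0 | 2.4% | 0.4% | 93.7% |
| 10% | 5.5% | 1.2% | 96.2% |
| 20% | 11.6% | 3.4% | 97.9% |
| 30% | 22.2% | 8.7% | 99.0% |

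At the planned rate, 141 × 0.03 = 4.23 complications are expected, so a loss of 10% to 30% is 0.4 to 1.3 events.

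**The case against.** The strongest reply is that the gate is narrower than it looks. Sites must report every device effect, serious or not, whether or not they link it to the scan, and the ADE definition covers malfunction, use error and misuse. The site's view on MRI causation is therefore not the filter. There are other safeguards:

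- Sites are told to evaluate for ADEs at each revision (Table 5).
- A significant threshold rise must be reported (6.5.2.2, 6.5.3.1).
- Sustained ventricular arrhythmia or asystole during the scan goes on an AE form (6.5.2.1).
- Explanted hardware is to be returned for analysis (6.8.1, 6.8.2).
- Monitors review source records (10.0) and a DSMB reviews accumulating data (14.2).
- The charter could contain a revision trigger.

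All of this stands, and it limits the size of the problem. It does not close the gap. None of these passages sends a revision to the CEC when the site sees no ADE, and the threshold rule does not cover dislodgment, sensing loss or a pocket revision.

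Three stronger readings are tempting, and the documents do not support them:

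- *A reader might infer that 8.2.1 tells sites most events need not be reported, and that revisions escape by that route.* Section 8.2.1 gives way to the rest of the CIP, and 8.2 and 8.2.2 require all ADEs. Its bullet also does not exempt events related to a revision procedure. What remains is a wording conflict: read literally, it would exempt a scan-caused embolism.
- *A reader might infer that the committee can only remove events from the site's list.* The CEC also receives ADEs that the site considers unrelated to MRI. It adjudicates from CRFs, medical records and its own judgment, so it can add endpoint events among those.
- *A reader might infer that every revision at least generates a System Revision CRF.* Complete explants (6.7) and pocket-only revisions (6.8) do not need one.

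**Conclusion.** The concern holds as a gap in the protocol's intake rule for the CEC. An invasive post-scan intervention that the site does not regard as an ADE can go unadjudicated, count as complication-free or leave the safety set, and drop out of both efficacy analyses. Any resulting error in the safety rate favors success.

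The size cannot be known from the documents. With at most 7 complications allowed in 141, one missed event is enough in a borderline result. The pass probabilities of 5.5% to 22.2% at the null rest on an assumed loss of 10% to 30%, applied to all complications. Deaths always reach the CEC, so the loss can apply only to the non-fatal ones. At the planned 3% rate the effect would be about one event or less.

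The conclusion is limited to the protocol text, since the CEC charter was not supplied. Even if the charter has a trigger, the rule belongs in the protocol, which defines the endpoint. The sample size is not in question.

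**What to change.** In 14.1, and in the charter to match, state that the CEC reviews every death and every invasive intervention on the ICD system from the study scan through the 1-month visit, whatever the site's attribution. This covers generator or lead revision, repositioning, replacement, explant and pocket revision. Use the System Revision and Product Out of Service CRFs, which are already collected, as triggers; the second picks up complete explants. Neither form is required for a pocket-only revision, so add a short mandatory report for those.

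Separately, reconcile the 8.2.1 bullet with 8.2 and 8.2.2. One possible wording would limit the exemption to events unrelated to the study lead, the ICD, the study MRI scan and any revision procedure on the system.

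The cost is wording in 8.2.1, 14.1 and the charter, one short report for pocket revisions, and a handful of extra case reviews by the existing committee. The sample size of 141 and the analysis method do not change.
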